6.2 IMPORTANT PROTOCOL DEVIATIONS

Data discrepancies and deviations from the CTP will be identified for all treated subjects.

Consistency check listings (for identification of deviations of time windows) and a list of protocol deviations (e.g. deviations in drug administration, in blood sampling times, etc.) will be provided to be discussed at the Report Planning Meeting (RPM). At this meeting, all manual deviations identified at the sites by the CRAs and deviations too complex to program will be reviewed by the trial team to decide which are considered important. For definition of important protocol deviations (iPD), and for the process of identification of these, refer to the Boehringer Ingelheim (BI) SOP "Identify and Manage Important Protocol Deviations (iPD)" (2).

Section 7.3 of the CTP: *Important protocol deviation (iPD) categories will be suggested in the TSAP, IPVs will be identified no later than in the Report Planning Meeting, and the IPV categories will be updated as needed.*

Due to SOP changes, the iPD categories are no longer suggested in TSAP, but included in an iPD specification file (3).

If any iPDs are identified, they are to be summarised into categories and will be captured in the iPD specification file and the decision log. The iPD specification file (e.g. the DV domain specifications) will be stored within the TMF in EDMS.

The iPDs will be summarized and listed in the CTR.

6.3 SUBJECT SETS ANALYSED

Section 7.3 of the CTP:

- *Treated set (TS): The treated set includes all subjects who were randomized and treated with at least one dose of study drug. The treated set will be used for safety analyses.*
- *Pharmacokinetic parameter analysis set (PKS): This set includes all subjects in the treated set (TS) who provide at least one PK endpoint that was defined as primary and was not excluded due to a protocol deviation relevant to the evaluation of PK or due to PK non-evaluability (as specified in the following subsection 'Pharmacokinetics'). Thus, a subject will be included in the PKS, even if he/she contributes only one PK parameter value for one period to the statistical assessment. Descriptive and model based analyses of PK parameters will be based on the PKS.*

[...]

Plasma concentration data and parameters of a subject will be included in the statistical pharmacokinetic (PK) analyses if they are not flagged for exclusion due to a protocol deviation relevant to the evaluation of PK (to be decided no later than in the Report Planning Meeting) or due to PK non-evaluability (as revealed during data analysis, based on the criteria specified below). Exclusion of a subject's data will be documented in the CTR.

Relevant protocol deviations may be

- *Incorrect trial medication taken, i.e. the subject received at least one dose of trial medication the subject was not assigned to*
- *Incorrect dose of trial medication taken*
- *Use of restricted medications*

Plasma concentrations and/or parameters of a subject will be considered as non-evaluatable, if for example

- *The subject experienced emesis that occurred at or before two times median t_{max} of the respective treatment (Median t_{max} is to be determined excluding the subjects experiencing emesis),*
- *A predose concentration is >5% C_{max} value of that subject*
- *Missing samples/concentration data at important phases of PK disposition curve*

Plasma concentration data and parameters of a subject which is flagged for exclusion will be reported with its individual values but will not be included in the statistical analyses. Descriptive and inferential statistics of PK parameters will be based on the PKS.

The descriptive analysis of PK concentrations will be based on the ADS ADPC as described at the beginning of [Section 7](#).

Table 6.3: 1 Subject sets analysed

Class of endpoint	Subject set	
	TS	PKS
Analyses of PK endpoints		X
Safety parameters	X	
Demographic/baseline parameters	X	
Important protocol deviations	X	
Disposition	X	
Exposure	X	

6.5 POOLING OF CENTRES

This section is not applicable, because the study was performed in only one centre.

6.6 HANDLING OF MISSING DATA AND OUTLIERS

Handling of missing data and outliers will be performed as described in the CTP, Section 7.5.

The only exceptions where imputation might be necessary for safety evaluation are AE dates. Missing or incomplete AE dates are imputed according to BI standards (see BI-KMED-BDS-HTG-0035) (4).

Missing data and outliers of PK data are handled according to BI standards (see BI-KMED-TMCP-MAN-0012 (5) and BI-KMED-TMCP-MAN-0014 (6)).

6.7 BASELINE, TIME WINDOWS AND CALCULATED VISITS

The baseline value is defined as the last measurement before administration of Otezla in each treatment period.

Section 6.1 of the CTP: *Study measurements and assessments scheduled to occur 'before' trial medication administration on Day 1 are to be performed and completed within a 3 h-period prior to the trial drug administration.*

The acceptable deviation from the scheduled time for vital signs and laboratory tests will be ± 45 min.

Adherence to time windows will be checked via the consistency check listings at the RPM.

Unscheduled measurements of laboratory data and vital signs data will be assumed to be repeat measurements of the most recent scheduled measurement (e.g. for follow-up or confirmation of a particular value). Therefore, unscheduled measurements will be assigned to the planned time point of the previous scheduled measurement.

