Statistical methods	
The assessment of bioequivalence will be based upon 2-sided 90% confidence intervals (CIs) for the ratios of the geometric means (test/reference) for the primary endpoints using an acceptance range of 80.00 to 125.00%. This method corresponds to the two one-sided t-tests procedure, each at a 5% significance level. The statistical model will be an analysis of variance (ANOVA) on the logarithmic scale including effects for sequence, subjects nested within sequences, period, treatment and metabolic state (fed or fasted) as well as the treatment-by-metabolic state interaction. CIs will be calculated based on the residual error from the ANOVA and quantiles from the t-distribution.
 
Descriptive statistics will be calculated for all endpoints.

Proprietary confidential information © 2020 Boehringer Ingelheim International GmbH or one or more of its affiliated companies

FLOW CHART

Period	Visit	Day	Planned time (relative to drug administration) [h:min]	Approximate clock time of actual day [h:min]	Event and comment	Safety laboratory ⁸	PK blood (Apremilast)	Vital signs (BP, PR)	Questioning for AEs and concomitant therapy ⁶
SCR	1	-23 to -1			Screening (SCR) ¹	A		x	
1/2/3/4/5 ⁷	2/3/4/5/6 ⁷	-1	-12:00	20:00	Admission to trial site	x ⁵			x
			-11:30	20:30	Snack (voluntary) ³				
		1	-1:00	07:00	Allocation to treatment ² (visit 2 only)	B ²	x ²	x ²	x ²
			-0:30	07:30	Start of high fat, high calorie breakfast prior to treatments T _{fed} and R1 _{fed}				
			0:00	08:00	Drug administration				
			0:30	08:30		x			
			1:00	09:00		x			
			1:30	09:30		x			
			2:00	10:00	240 mL fluid intake	x		x	
			2:30	10:30		x			
			3:00	11:00		x			
			3:30	11:30		x			
			4:00	12:00	240 mL fluid intake	x		x	
			5:00	13:00	Lunch ³	x			
			6:00	14:00		x			
			8:00	16:00		x			
			10:00	18:00	Dinner				
			11:00	19:00		x			
			15:00	23:00		x		x	
		2	24:00	08:00	Breakfast (voluntary) ³ , discharge from trial site	B	x	x	x
			36:00	20:00	Ambulatory visit		x		x
			48:00	08:00	Ambulatory visit		x		x
FU	7	5 to 11			End of trial (EoTrial) examination ⁴	C		x	x

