1. Subject must be informed and written informed consent obtained prior to starting any screening procedures. Screening procedures include physical examination, check of vital signs, ECG, safety laboratory (including pregnancy test in women and drug screening), demographics (including determination of body height and weight, smoking status and alcohol history), relevant medical history, concomitant therapy and review of inclusion/exclusion criteria. Pharmacogenetic samples will be collected if needed.
2. The time is approximate; the procedure is to be performed and completed within 3h prior to drug administration.
3. If several actions are indicated at the same time, the intake of meals will be the last action.
4. At the end of trial visit the EoTrial examination includes physical examination, vital signs, ECG, safety laboratory (including pregnancy test in women), recording of AEs and concomitant therapies.
5. Only urine drug screening and alcohol breath test as well as pregnancy test in women will be done at this time.
6. AEs and concomitant therapies will be recorded throughout the trial, but will be specifically asked for at the times indicated in the Flow Chart above.
7. Five identical periods /visits separated by wash-out periods of at least 5 days between the administrations of apremilast.
8. Letter A, B and C define different sets of safety laboratory examinations (see Section [5.2.3](#))

TABLE OF CONTENTS

TITLE PAGE	1
CLINICAL TRIAL PROTOCOL SYNOPSIS	2
FLOW CHART	4
TABLE OF CONTENTS	5
ABBREVIATIONS	9
1. INTRODUCTION.....	12
1.1 MEDICAL BACKGROUND.....	12
1.2 DRUG PROFILE	13
1.2.1 Apremilast	13
1.2.2 Residual Effect Period	14
1.3 RATIONALE FOR PERFORMING THE TRIAL	14
1.4 BENEFIT - RISK ASSESSMENT	14
1.4.1 Procedure-related risks	15
1.4.2 Drug-related risks and safety measures.....	15
2. TRIAL OBJECTIVES AND ENDPOINTS.....	18
2.1 MAIN OBJECTIVES, PRIMARY AND SECONDARY ENDPOINTS	18
2.1.1 Main objectives.....	18
2.1.2 Primary endpoints	18
2.1.3 Secondary endpoint	18
2.2.2.2 Safety and tolerability	19
3. DESCRIPTION OF DESIGN AND TRIAL POPULATION.....	20
3.1 OVERALL TRIAL DESIGN AND PLAN	20
3.2 DISCUSSION OF TRIAL DESIGN, INCLUDING THE CHOICE OF CONTROL GROUP.....	21
3.3 SELECTION OF TRIAL POPULATION	21
3.3.1 Main diagnosis for trial entry	21
3.3.2 Inclusion criteria	21
3.3.3 Exclusion criteria	22
3.3.4 Withdrawal of subjects from treatment or assessments	24
3.3.4.1 Discontinuation of trial treatment	24

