5.2.3 Safety laboratory parameters

For the assessment of laboratory parameters, blood and urine samples will be collected by the trial site at the times indicated in the Flow Chart after the subjects have fasted for at least 9 h. For retests, at the discretion of the investigator or designee, overnight fasting is not required.

The parameters that will be determined are listed in Tables [5.2.3: 1](#) and [5.2.3: 2](#). Reference ranges will be provided in the ISF, Section 10.

Manual differential white blood cell count or urine sediment examinations will only be performed if there is an abnormality in the automatic blood cell count or in the urinalysis, respectively.

Proprietary confidential information © 2020 Boehringer Ingelheim International GmbH or one or more of its affiliated companies

Table 5.2.3: 1

Routine laboratory tests

Functional lab group	BI test name [comment/abbreviation]	A ¹	B ¹	C ¹
Haematology	Haematocrit Haemoglobin Red Blood Cell Count/Erythrocytes White Blood Cells/Leucocytes Platelet Count/Thrombocytes (quant)	X X X X X	X X X X X	X X X X X
Automatic WBC differential, relative	Neutrophils/Leukocytes; Eosinophils/Leukocytes; Basophils/Leukocytes; Monocytes/Leukocytes; Lymphocytes/Leukocytes	X	X	X
Automatic WBC differential, absolute	Neutrophil, absol.; Eosinophils, absol.; Basophils, absol.; Monocytes, absol.; Lymphocytes, absol.	X	X	X
Manual differential WBC (if automatic differential WBC is abnormal)	Neut. Poly (segs); Neut. Poly (segs), absol.; Neutrophils Bands; Neutrophils Bands, absol.; Eosinophils/Leukocytes; Eosinophils, absol.; Basophils/ Leukocytes; Basophils, absol.; Monocytes/ Leukocytes; Monocytes, absol.; Lymphocytes/Leukocytes; Lymphocytes, absol.			
Coagulation	Activated Partial Thromboplastin Time Prothrombin time Prothrombin time – INR (International Normalization Ratio)	X X X	-- -- --	X X X
Enzymes	AST [Aspartate transaminase] /GOT, SGOT ALT [Alanine transaminase] /GPT, SGPT Alkaline Phosphatase Gamma-Glutamyl Transferase Creatine Kinase [CK] Creatine Kinase Isoenzyme MB [only if CK is elevated]	X X X X X X	X X X X -- --	X X X X X X
Hormones	Thyroid Stimulating Hormone	X	--	--
Substrates	Glucose (Plasma) Creatinine Bilirubin, Total Bilirubin, Direct Protein, Total C-Reactive Protein (Quant) Cholesterol, total Triglyceride	X X X X X X X	X X X X X -- --	X X X X X X X
Electrolytes	Sodium Potassium	X X	X X	X X

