5.2.6.2 Adverse event collection and reporting

5.2.6.2.1 AE collection

Upon enrolment into a trial, the subject's baseline condition is assessed (for instance, by documentation of medical history/concomitant diagnoses), and relevant changes from baseline are noted subsequently.

Subjects will be required to report spontaneously any AEs as well as the time of onset, end time, and intensity of these events. In addition, each subject will be regularly assessed by the medical staff throughout the clinical trial and whenever the investigator deems necessary. As a minimum, subjects will be questioned for AEs (and concomitant therapies) at the time points indicated in the [Flow Chart](#). Assessment will be made using non-specific questions such as 'How do you feel?'. Specific questions will be asked wherever necessary in order to more precisely describe an AE.

A carefully written record of all AEs shall be kept by the investigator in charge of the trial. Records of AEs shall include data on the time of onset, end time, intensity of the event, and any treatment or action required for the event and its outcome.

The following must be collected and documented on the appropriate CRF(s) by the investigator:

- From signing the informed consent onwards until an individual subject's end of trial:
 - All AEs (serious and non-serious) and all AESIs
 - The only exception to this rule are AEs (serious and non-serious) and AESIs in Phase I trials in healthy volunteers, when subjects discontinue from the trial due to screening failures prior to administration of any trial medication. In these cases, the subjects' data must be collected at trial site but will not be entered in the CRF or trial database and will not be reported in the CTR.
- After the individual subject's end of trial:
 - The investigator does not need to actively monitor the subject for AEs but should only report any occurrence of cancer and related SAEs and related AESIs of which the investigator may become aware of by any means of communication, e.g. phone call. Those AEs should, however, not be reported in the CRF.

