7.8.2 Laboratory data

The analyses of laboratory data will be descriptive in nature and will be based on BI standards [BI-KMED-BDS-HTG-0042] ([13](#)).

Laboratory data will be analysed qualitatively via comparison of laboratory data to their reference ranges. Values outside the reference range as well as values defined as possibly clinically significant will be flagged in the data listings.

Clinically relevant findings in laboratory data will be reported as baseline conditions (at screening) or as AEs (during the trial) if judged clinically relevant by the investigator, and will be analysed as such.

It is the investigator's responsibility to decide whether a lab value is clinically significantly abnormal or not (at the RPM at the latest).

Descriptive statistics of laboratory data including change from baseline will be calculated by planned time point based on the worst value of the subject at that planned time point (or assigned to that planned time point).

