7.8.3 Vital signs

Descriptive statistics over time including change from baseline will be performed for vital signs (blood pressure and pulse rate). In the listing the difference from baseline will also be displayed.

For vital signs, descriptive statistics will be calculated by planned time point based on the last value of the subject at that planned time point (or assigned to that planned time point).

Clinically relevant findings in vital signs will be reported as AEs.

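### SAP 6.7 can place an unscheduled post-dose laboratory or vital-sign value in the pre-dose row of the safety tables, and then in no post-dose row

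*SAP*

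**What the plan says.** SAP 6.7 treats every unscheduled laboratory or vital-sign value as a repeat of the latest scheduled one, so that "unscheduled measurements will be assigned to the planned time point of the previous scheduled measurement". The reason it gives is follow-up or confirmation of a value. It sets no condition about dosing.

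The same section defines baseline separately: "The baseline value is defined as the last measurement before administration of Otezla in each treatment period".

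Two further rules decide which value enters each row of the tables:

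- Laboratory data (SAP 7.8.2): "based on the worst value of the subject at that planned time point (or assigned to that planned time point").
- Vital signs (SAP 7.8.3): "based on the last value of the subject at that planned time point (or assigned to that planned time point").

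In the protocol's Flow Chart, laboratory set B appears in each period at -1:00 and at 24:00, the latter in the row marked "discharge from trial site". Footnote 2 fixes the earlier one as truly pre-dose: "The time is approximate; the procedure is to be performed and completed within 3h prior to drug administration".

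**The concern.** Treating an unscheduled value as a repeat of the previous scheduled one is reasonable while the subject's exposure has not changed. Once a dose has been given, it has changed. A sample taken because of symptoms after dosing does not repeat the pre-dose sample, yet the rule files it there.

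The value has only one planned time point, so it cannot also appear after dosing. A possible drug effect then moves out of the post-dose summary and into the row it would be compared with. The SAP also ends up with two meanings of pre-dose. Baseline is set by the actual time of dosing and the pre-dose row is not, so the two can differ for the same subject and period.

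After early termination, safety is one of the main things still to be reported (SAP 4).

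**Working it through.** The documents give no figure on this point to reproduce. The check applies the rules to the schedule and then sizes the effect.

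**Step 1: the exposed window.** Inputs are the Flow Chart and its footnote 2.

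- Laboratory: set B is planned before dosing and next at 24:00, so the window is 24 - 0 = 24 h per dose.
- Vital signs: also planned before dosing. In the extracted Flow Chart the mark at 2:00 may be vital signs or AE questioning. The window is 2 - 0 = 2 h on the first reading and up to 24 - 0 = 24 h on the second.

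**Step 2: a search for an exception.**

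- The baseline definition in SAP 6.7 looks at the actual time of dosing, but it governs only the baseline value.
- Protocol 7.3.4 assigns measurements to treatment by planned time, which reinforces the rule. Read literally, a Period 1 post-dose value moved to the pre-dose time point would count as screening.
- Nothing confines unscheduled measurements to the time before dosing. Protocol 5.2.3 states: "For retests, at the discretion of the investigator or designee, overnight fasting is not required". Protocol 5.2.6.2.1 states: "each subject will be regularly assessed by the medical staff throughout the clinical trial and whenever the investigator deems necessary". Protocol 6.2.3 has clinically relevant abnormal values monitored until acceptable.

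**Step 3: which value is tabulated.** For vital signs, the moved value is the last one assigned to the pre-dose row and replaces the true value. For laboratory data it replaces the true value only if it is worse; otherwise it enters no summary row.

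**Step 4: size.** The pre-dose mean shifts by

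shift = k × (U - P) / n

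Here k is the number of affected subjects, U the unscheduled value, P the true pre-dose value and n the number of subjects in the column. SAP 4 gives 20 subjects in total, so n is at most 20 and one subject carries at least 1/20 = 5% of the difference. The documents give no rate of unscheduled tests, so k, U and P are assumed. For ALT, higher is taken as worse.

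| Case (n = 20) | Calculation | Shift of pre-dose mean |
|---|---|---|
| ALT, no subject affected | 0 × 65 / 20 | 0 |
| ALT 90 against 25, one subject | (90 - 25) / 20 | +3.25 U/L |
| ALT 90 against 25, two subjects | 2 × 65 / 20 | +6.5 U/L |
| ALT difference of 10, one subject | 10 / 20 | +0.5 U/L |
| ALT difference of 100, one subject | 100 / 20 | +5.0 U/L |
| ALT 20 against 25 (not worse) | worst value stays 25 | 0 |
| Pulse 95 against 60, one subject | (95 - 60) / 20 | +1.75 bpm |
| Pulse 55 against 60, one subject | (55 - 60) / 20 | -0.25 bpm |

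SAP 7 also reports minimum and maximum. In the one-subject ALT example the pre-dose maximum becomes 90 unless another pre-dose value is higher, and that subject shows a change from baseline of 90 - 25 = 65 U/L at a pre-dose time point.

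**The case against.** The strongest reply is that the rule is a reasoned convention, agrees with the planned-time principle of protocol 7.3.4, and changes no conclusion.

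- **Evidence of occurrence is weak.** A retest is by nature a repeat, as SAP 6.7 assumes. The provision for assessment when the investigator sees a need concerns AE questioning. The explicit provision for unscheduled safety recordings (protocol 5.2.4) covers ECGs, to which this rule does not apply. This stands as a limit on frequency. It does not exclude post-dose checks, and the rule gives a wrong row whenever one occurs.
- **The layout is not shown.** If the tables print one baseline row and no separate pre-dose row, the baseline definition governs and no pre-dose row is distorted. This is possible, but both safety sections ask for statistics by planned time point, and the value would still be missing from every post-dose row.
- **Other text may restrict the rule.** The company laboratory standard, the technical TSAP and a blacked-out SAP contents entry between 6.7 and 7 could not be read. This stands as a caveat.
- **The effect is small.** Safety analysis is descriptive, individual values are listed, out-of-range laboratory values are flagged, and clinically relevant findings are reported as AEs. All of this is correct and limits the consequence to the tables.
- **The remedy can misattribute too.** A retest soon after dosing that only confirms an abnormal pre-dose value would be shown as post-dose. This is a real cost, though a separate label keeps such values visible for what they are.

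**Conclusion.** The concern holds. Followed exactly, SAP 6.7 with 7.8.2 and 7.8.3 can put a post-dose value in the pre-dose row of the by-time-point tables and in none of the post-dose rows. This is a stated rule that misfiles a value when a dose intervenes, rather than a missing detail.

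The size depends on whether such values exist. With none the effect is zero. With one, the pre-dose mean moves by at least 5% of the difference, and the pre-dose minimum or maximum can be set by that value. Baseline, changes at scheduled post-dose times, listings, AE reporting and the pharmacokinetic results are not touched.

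The conclusion assumes that the unseen standards and redacted text do not already restrict the rule. Confidence is medium. The change should be made because it is cheap and safety tables are a main remaining output.

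**What to change.** Replace the last sentence of SAP 6.7 with:

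> An unscheduled measurement is assigned to the planned time point of the previous scheduled measurement only if no administration of Otezla lies between them. Otherwise it is attributed by actual time to the treatment just given, is not summarised at a pre-dose time point, and is shown under a separate label, *unscheduled post-dose*.

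Add a line to SAP 4 recording that attribution by actual time for these values departs from the planned-time principle of protocol 7.3.4. If the company standard or technical TSAP already contains this restriction, a cross-reference in SAP 6.7 is enough.

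The cost is two sentences, one line and a small change to the derivation. The drawbacks are that a purely confirmatory retest taken after dosing appears as post-dose, the extra row will hold few subjects, and a deviation from the protocol has to be noted.
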